4.0 STUDY OVERVIEW AND STUDY PROCEDURES

4.1 Study Overview

This is a Phase 3 randomized double-blind, placebo controlled trial comparing the efficacy and safety of ABT-414 versus placebo, each as concurrent treatment with standard-of-care therapy of radiation therapy/TMZ plus adjuvant TMZ and followed by ABT-414/placebo monotherapy, in subjects with newly diagnosed GBM.

The study comprises a Screening Period of up to 7 weeks from surgery/biopsy; a 6-week concomitant Chemoradiation Phase; an Adjuvant Phase beginning approximately 4 weeks after completion of chemoradiation, and a Follow-Up Phase. The Adjuvant Phase is comprised of 28-day cycles, with subjects receiving concomitant TMZ and study drug (ABT-414/placebo) for the first 6 cycles, and study drug (ABT-414/placebo) monotherapy for the following 6 cycles. Subsequent cycles will start approximately 28 days from the start of the previous cycle, and the cycle schedule will not be affected by delays or interruptions in TMZ or ABT-414/placebo dosing. Adjuvant treatment will be discontinued once disease progression has been determined. A Final Study Drug Visit will be performed upon discontinuation of study drug (ABT-414/placebo) for any reason, followed by 35-Day and 49 Day Follow-Up Visit (± 3 days). If subjects are unable to attend the 49 Day Follow-Up Visit, a phone call should be performed to obtain adverse event and concomitant medication information. In the Follow-Up Phase, subjects who complete adjuvant treatment or discontinue study drug prior to disease progression will continue to undergo MR imaging and assessment of neurocognitive functioning and PRO approximately every 8 weeks up to and including at the time of disease progression, starting 8 weeks after the last scheduled PRO assessments in the Adjuvant Phase. After disease progression, overall survival will continue to be assessed quarterly.

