- c. As per TMZ prescribing information, during the 28-day cycle of TMZ, a blood count for ANC and platelets should be performed 21 days (\pm 2 days) after the start of each TMZ cycle. If the ANC falls below 1,500/ μ L or if the platelet count falls below 100,000/ mm^3 , then blood counts should be performed weekly until recovery to these levels before TMZ dosing. A certified local lab may be used instead of central lab; if so, ANC and platelet results should be reported in the eCRF. Day 22 testing may be omitted for cycles in which TMZ is not administered or if local prescribing information allows for a different testing schedule for ANC and platelets.
- d. Final Study Drug Visit to be performed approximately 14 days after last dose of ABT-414/placebo. The physical examination and MR imaging from the first visit of the Follow-Up Phase will be used for the Final Study Drug Visit if these visits coincide (e.g., if the subject completes 12 cycles of Adjuvant Phase).
- e. To be performed 35 days (\pm 3 days) after the last dose of study drug (placebo or ABT-414). If the Final Study Drug Visit is more than 35 days after the last dose of study drug, then 35-day safety follow-up procedures will not be performed.
- f. Visits in Follow-Up Phase to occur every 8 weeks, beginning 8 weeks after Day 1 of the last odd-numbered cycle in the Adjuvant Phase.
- g. Height will be assessed at Screening only. Weight will be collected at all visits. Complete physical examination will be performed at Screening only. Symptom directed physical examination will be performed at all other designated visits as clinically indicated.
- h. Ophthalmology exam to be performed prior to ABT-414/placebo dosing on Day 1 (or up to 7 days prior to Day 1) of Cycle 1, Cycle 2, and every odd-numbered cycle thereafter (Cycles 3, 5, 7, etc.). Ophthalmology exam for Cycle 1 Day 1 may be omitted if the subject had no corneal microcysts or ocular adverse events during or after the Chemoradiation Phase. Ophthalmology exams may be discontinued if the subject has been on Level 1 eye drops with no ocular toxicity for 2 consecutive eye exams.
- i. Ophthalmology exam at Day 35 Follow-Up Visit to be done only if subject had corneal microcysts or other ocular findings related to ABT-414 or ocular steroids on previous exam and repeated at least every 8 weeks until satisfactory resolution of eye toxicities.

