5.3.1.2 Adjuvant Treatment

TMZ will be administered orally once per day for 5 consecutive days (Days 1 – 5) of a 28-day (+/- 3 day) cycle. The starting dose for the first cycle will be 150 mg/m²/day, with a single dose escalation to 200 mg/m²/day in subsequent cycles if no treatment-related adverse events > Grade 2 are noted. The timing of each daily dose will be at the discretion of the Investigator.

The start of the first cycle will be scheduled approximately 28 days after the last day of radiotherapy. The start of all subsequent cycles (Cycles 2 – 12) will be scheduled every 4 weeks (28 days ± 3 days) after the first daily dose of TMZ of the preceding cycle.

The dose will be determined using the BSA calculated at the beginning of each treatment cycle. The BSA will be calculated from the height obtained at the screening visit and from the weight

obtained at the visit immediately before each cycle. More frequent assessment and use of height and/or weight and calculation of BSA are permitted throughout the study. The dose of TMZ does not have to be adjusted unless there has been at least a 10% change in body weight; recalculation of dose for < 10% weight changes is allowed at the discretion of the Investigator. The dose will also not be capped for those that are overweight. The daily dose will be rounded to the nearest 5 mg (where dosage strengths are available to accommodate rounding to 5 mg). The exact dose administered should be recorded in the eCRF. Each daily dose should be given with the least number of capsules.

Prior to each treatment cycle with TMZ a complete blood count (CBC) will be obtained (within 72 hours prior to dosing). Subjects should be instructed to fast at least 2 hours before and 1 hour after TMZ administration. Water is allowed during the fast period. Subjects will be instructed to swallow the capsules whole, in rapid succession, without chewing them.

If vomiting occurs during the course of treatment, no re-dosing of the subject is allowed before the next scheduled dose.

Antiemetic prophylaxis with a 5-HT3 antagonist is strongly recommended and should be administered 30 to 60 minutes before TMZ administration (Section 5.8).

IV temozolomide (as per local institutional standard) may be used instead of oral TMZ if there is a change in the subject's social situation (e.g., move to a nursing home or changes in drug reimbursement) after treatment TMZ initiation such that oral dosing of temozolomide is no longer possible.

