8.3.2 Post-Radiation (Adjuvant) Temozolomide

Continued dosing administration is based on adverse events (AEs) during the prior treatment cycle. If multiple AEs are seen, the dose administered should be based on the dose reduction required for the most severe grade of any single AE.

Dose Level	Temozolomide Dose, mg/m ² /day	Remarks
-1	100	Reduction if prior AE
0	150	Starting dose cycle 1 (adjuvant)
+1	200	Escalated dose at cycle 2, for cycles 2 – 12 in absence of AE

Delay

On Day 1 of each cycle (within the prior 72 hours), ANC $\geq 1.5 \times 10^9/L$, platelet count $\geq 100 \times 10^9/L$ and all treatment-related grade 3 or 4 non-hematologic AEs (except alopecia, nausea, and vomiting) must have resolved (to grade ≤ 1).

If AEs persist, treatment should be delayed by 2 weeks for up to 4 consecutive weeks, so that the TMZ dosing can coincide with the administration of the ABT-414 or placebo. If, after 4 weeks of delay, all AEs have still not resolved, then any further adjuvant treatment with TMZ should be stopped. When possible, TMZ treatment when resumed should start on either Day 1 or Day 15 of a cycle so that it may coincide with ABT-414/placebo treatment.

Dose Escalation

If, during the first cycle, all non-hematologic AEs observed were grade ≤ 2 (except alopecia, nausea and vomiting) and with platelets $\geq 100 \times 10^9/L$ and ANC $\geq 1.5 \times 10^9/L$, then the TMZ dose should be escalated to dose level 1 and this dose should be used as the starting dose for subsequent cycles. If treatment after cycle 1 has to be delayed because of ongoing non-hematologic AEs of grade ≥ 2 , then no escalation is possible. If the dose was not escalated at cycle 2, then the dose should not be escalated in further cycles (Cycles 3 – 6).

Dose Reductions

If any non-hematologic AE observed was grade > 2 (except alopecia, nausea and vomiting) and/or if platelets $< 50 \times 10^9/L$ and/or ANC $< 1 \times 10^9/L$, then the dose should be reduced by one dose level. For subjects who would require dose reductions to a dose level $< 100 \text{ mg/m}^2/\text{day}$, TMZ will be stopped. Also, if any of the same non-hematologic grade 3 AE recurs (except alopecia, nausea and vomiting) after reduction for that AE, then TMZ will be stopped.

If any treatment-related non-hematologic AE observed was grade 4 (except alopecia, nausea and vomiting) then adjuvant TMZ treatment should be stopped.

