Subsequent cycles (Cycles 3 – 12): Any dose reductions of TMZ will be determined according to (1) non-hematologic AE during the preceding treatment cycle, as well as (2) the nadir (lowest/worst) ANC and platelet counts observed. No dose escalation should be attempted. The same dose reductions as for the second cycle should be applied.

Important: If the dose was reduced or delayed for adverse events, there will be no dose escalation.

The reason(s) for dose reduction and/or delay must be documented in the eCRF.

Summary of Dose Modification or Discontinuation During Post-Radiation Temozolomide

Worst Non-Hematologic AE (Except Alopecia, Nausea and Vomiting) During the Previous Cycles	
Grade	Dose Modification
0 – 2	No dose modifications for non-hematologic AEs. Dose escalations (only for cycle 2) or reductions based on ANC and platelet counts are applicable.
3	Reduce by one dose level (except alopecia, nausea and vomiting). Dose modifications (escalations or reductions) based on ANC and platelet counts are not applicable. No further escalation is possible. If the same non-hematologic grade 3 AE recurs (except alopecia, nausea and vomiting) after reduction for that AE, then stop temozolomide.
4	Stop temozolomide (except for alopecia, nausea and vomiting). Dose modifications (escalations or reductions) based on ANC and platelet counts are not applicable.

Nadir Values

ANC	Action
$\geq 1.5 \times 10^9/L$	Escalation to DL 1 (cycle 2 only)
$\geq 1 \text{ \& } < 1.5 \times 10^9/L$	Dose unchanged
$< 1 \times 10^9/L$	Reduce by 1 dose level
Platelets	
$\geq 100 \times 10^9/L$	Escalation to DL 1 (cycle 2 only)
$50 - 99 \times 10^9/L$	Dose unchanged
$< 50 \times 10^9/L$	Reduce by 1 dose level

Note: A complete blood count must be performed on Day 22 (+/- 3 days) of each adjuvant treatment cycle.

Hematologic AE on Day 1 of Each Cycle (Within 72 Hours Before)

AE	Delay
ANC $< 1.5 \times 10^9/L$ and/or Platelet count $< 100 \times 10^9/L$	Delay up to 4 weeks until all resolved. If unresolved after 4 weeks then stop temozolomide. If resolved, dose delay/reductions based on non-hematologic AEs are applicable. If treatment has to be delayed for AEs, then no escalation is possible.

Non-Hematological AE (Except for Alopecia, Nausea and Vomiting) on Day 1 of Each Cycle (Within 72 Hours Before)

Grade	Delay

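### After a 2-week adjuvant TMZ delay with a Day 15 restart, Protocol Section 4.1 implies the next course on Day 29 and Section 5.3.1.2 implies Day 43

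*Protocol*

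**What the plan says.** Four rules in the current protocol bear on when TMZ is next given after a delay.

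- **Cycle calendar.** Section 4.1, repeated in the synopsis (Appendix II), starts each adjuvant cycle about 28 days after the start of the one before and adds that "the cycle schedule will not be affected by delays or interruptions in TMZ or ABT-414/placebo dosing".
- **Days of dosing.** Section 4.1 gives TMZ on Days 1 to 5 of each 28-day cycle. The same cycles carry ABT-414/placebo on Days 1 and 15.
- **Start of later cycles.** Section 5.3.1.2 has Cycles 2 to 12 "scheduled every 4 weeks (28 days ± 3 days) after the first daily dose of TMZ of the preceding cycle".
- **Delay and restart.** If adverse events persist on Day 1, Section 8.3.2 says that "treatment should be delayed by 2 weeks for up to 4 consecutive weeks". It adds, subject to feasibility, this rule: "TMZ treatment when resumed should start on either Day 1 or Day 15 of a cycle so that it may coincide with ABT-414/placebo treatment".

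Two blood-count rules depend on the same calendar. Table 2 note c says "a blood count for ANC and platelets should be performed 21 days" (± 2 days), counted from the first day of the TMZ cycle. The note under the nadir table in Section 8.3.2 says "A complete blood count must be performed on Day 22 (+/- 3 days) of each adjuvant treatment cycle".

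**The concern.** A 2-week delay counted from Day 1 lands on Day 15, so the protocol itself directs this case. It then gives two answers for the following course. Under Section 4.1 a TMZ delay moves nothing, and TMZ falls due again on the next Day 1. Under Section 5.3.1.2 the next cycle is timed from the TMZ dose, so a delayed dose moves it.

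The patients affected have just been delayed for low counts or another toxicity. A site that follows one section departs from the other. The adjuvant TMZ dose rules also use the lowest counts of the preceding cycle, so the timing of the count relative to the course matters too.

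**Working it through.** Let Day 1 be the Day 1 on which the delayed course was due. Let *r* be the day on which TMZ actually starts, so the 5-day course runs from *r* to *r* + 4.

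**Inputs**
- Cycle length 28 days; TMZ on Days 1 to 5 (Section 4.1).
- Calendar not moved by delays (Section 4.1, synopsis).
- Next cycle 28 ± 3 days after the first TMZ dose (Section 5.3.1.2).
- Delay of 2 weeks, up to 4 weeks; restart on Day 1 or Day 15 (Section 8.3.2).

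**Formulas**
- Fixed calendar: next course = first of Days 1, 29, 57, ... after *r*.
- TMZ-anchored: next course = *r* + 28.
- TMZ-free days = next course − (*r* + 4) − 1.

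**No delay, *r* = 1 (the plan's own interval).** Fixed: Day 29. Anchored: 1 + 28 = Day 29. Both give 28 days between starts and 29 − 5 − 1 = 23 TMZ-free days, which reproduces the stated 28-day interval.

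**2-week delay, *r* = 15**

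| | Fixed calendar (4.1) | TMZ-anchored (5.3.1.2) |
|---|---|---|
| Next course | Day 29 | 15 + 28 = Day 43 (window 40 to 46) |
| Interval from restart | 29 − 15 = 14 days | 28 days (25 to 31) |
| TMZ-free days | 29 − 19 − 1 = 9 | 43 − 19 − 1 = 23 |
| Day of the fixed cycle | Day 1 | 43 − 28 = Day 15 |

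The two answers differ by 43 − 29 = 14 days, against a window of ± 3 days.

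**4-week delay, *r* = 29.** Fixed: Day 57. Anchored: 29 + 28 = Day 57. There is no conflict.

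**Blood counts after a Day 15 restart.** On the fixed calendar, the Day 22 count falls 22 − 15 = 7 days after TMZ starts. The 21-day count falls on 15 + 21 = Day 36, which is Day 8 of the next fixed cycle. That is after a Day 29 course has begun but before a Day 43 course.

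**Why no schedule meets every passage.** Day 29 meets the fixed calendar and Days 1 to 5 dosing but breaks the 28 ± 3 day rule. Day 43 on an unmoved calendar meets the 28-day rule but puts TMZ on Day 15, outside Days 1 to 5. Moving the whole cycle so that Day 43 becomes Day 1 contradicts the fixed calendar.

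**The case against.** The strongest reply is that TMZ can be read as running on its own 28-day calendar. Table 2 note c speaks of a TMZ cycle, and 21 days after TMZ Day 1 is Day 22 of that cycle, so on this reading the two blood-count rules agree. TMZ would continue on Day 15 of the fixed cycles while the infusions and visits stay put. This is coherent, and it shows that the blood-count split follows from the main ambiguity and is not a separate error. But no text defines two calendars. Section 4.1 uses one set of cycles for both drugs, and Table 2 lists TMZ under Day 1.

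Other points on that side:

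- **Safeguards.** A blood count is required within 72 hours before each TMZ cycle, with thresholds for neutrophils, platelets and adverse events, and counts are weekly after a fall below threshold. Nobody is re-dosed on the calendar alone. This stands, but none of these checks sets a minimum interval.
- **Wording of the restart.** It applies only when possible. This stands, but Day 15 remains where a 2-week delay lands.
- **Local prescribing information.** Section 8.3 lets it replace Section 8.3.1 or 8.3.2 where they conflict. That does not settle Section 4.1 against Section 5.3.1.2.
- **Reach.** SAP Section 6.0 has main-study enrolment complete by 19 March 2018. Without delays, 7 + 4 + 48 = 59 weeks brings planned TMZ to an end around early May 2019, before the synopsis date of 26 May 2019. The number still exposed may be small. However, the SAP describes the China cohort as still enrolling, and Appendix X keeps TMZ on Days 1 to 5 and repeats the 21-day count.

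A reader might also infer more than the documents support:

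- **Doubled TMZ dose intensity.** If the previous course began on Day 1 of the preceding cycle (Day −27 by simple subtraction, 28 days before Day 1), the delay made a 42-day gap. The two intervals then average (42 + 14)/2 = 28 days.
- **Two compliant sites at different intervals.** A course at 14 days would itself breach Section 5.3.1.2.
- **More of these delays on ABT-414.** The interim summary in Section 1.0 reports more thrombocytopenia on that arm but gives no delay rates.
- **Drifting scans.** Section 4.2 already keeps tumor assessments on schedule regardless of therapy delays. For PRO and neurocognitive data, the windows of about ± 4 weeks in SAP Section 7.5.1 would absorb a single 14-day shift of a visit otherwise on schedule.

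**Conclusion.** The contradiction stands, confined to a 2-week adjuvant TMZ delay with a Day 15 restart. The next course falls on Day 29 by one section and Day 43 by another, a 14-day difference that the ± 3-day window cannot cover. Neither date is printed in the protocol: Day 29 follows from the fixed calendar plus Days 1 to 5 dosing, and Day 43 from adding 28 days to the restart. Both take the word cycle to mean the study cycle in all the passages. The divergence in blood counts (Day 22 against Day 36) holds only if the Section 8.3.2 note is read on the fixed calendar.

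This is a conflict between stated rules, not a missing detail, and it concerns patients who have just had toxicity, so it should be corrected. The documents do not support a claim of doubled dose intensity, arm imbalance or scan drift. Sample size, power, alpha and the OS analysis do not depend on it. No view is taken here on which interval is right.

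**What to change.** In one amendment:

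1. Reconcile Section 4.1 (both the fixed-calendar sentence and the Days 1 to 5 wording), the matching synopsis text, Section 5.3.1.2 and Section 8.3.2, so that one stated anchor sets the next TMZ course after a Day 15 restart. The choice of interval is the sponsor's.
2. Tie the counts in Table 2 note c and the Section 8.3.2 note to that anchor, and carry the wording into the corresponding notes in Appendices IX and X.
3. Confirm that PRO and neurocognitive visits stay on the original cycle calendar, as Section 4.2 already does for tumor assessments.

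The cost is a few sentences. No new procedure is needed.

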4.2 Study Procedures

The study procedures outlined in [Table 1](#) and [Table 2](#) are discussed in detail in this section with the exception of the monitoring of treatment compliance (Section [5.10](#)) and the collection of adverse event information (Section [7.0](#)). All study data will be recorded on electronic case report forms (eCRFs), with the exception of pregnancy reporting forms and the neurocognitive function tests.

Procedures performed at Screening will serve as baseline, unless repeated prior to dosing; in which case the latter will serve as baseline. Unless otherwise noted, subsequent study procedures should be performed within 3 days prior to the scheduled study visit date when possible. Subjects who are not randomized will be considered a screen failure and will not be included in any intent-to-treat analyses.

Informed Consent

The informed consent for tissue and other pre-screening and for activities in the main study may be used separately or combined as a single informed consent document where allowed by local regulation and the IEC/IRB.

The IEC/IRB-approved informed consent must be signed and dated by each subject or the subject's legally acceptable representative prior to the submission of tumor tissue for screening, undergoing any study procedures or before any prohibited medications are withheld from the subject in order to participate in this study. Separate informed consent documents will also be required for the optional substudies in this protocol: for the collection of pharmacogenetic samples and the collection of tumor tissue post-treatment after disease progression, Section [15.3](#).

Tumor tissue testing will be conducted to confirm GBM diagnosis (central review of tumor histopathology), determination of *EGFR* amplification, *EGFRvIII* mutation and *MGMT* methylation status are all required for subject randomization. All clinical screening procedures should proceed simultaneously while tissue testing results are pending and should not be delayed until after EGFR amplification status is obtained.

For details on obtaining and documenting informed consents, Section [15.3](#).

Medical and Oncologic History

The following will be collected during the Screening Visit:

- Demographic information, including age, sex, and ethnicity. Ethnicity will include whether a subject is first generation Han Chinese.

- Complete medical history, including documentation of any clinically significant medical condition.
- History of tobacco and alcohol use.
- Detailed oncologic history including:
 - Date of primary cancer diagnosis;
 - Histology at the time of study entry;
 - Date and extent of surgical resection;
 - Neurologic deficits, if any, at the time of enrollment;

At each visit, the subject's medical history will be reviewed, and any changes from baseline will be recorded in the source documents and on the adverse event eCRF. On Day 1, any changes observed from the Screening Visit will be recorded in the subject's medical history.

Physical Examination

A complete physical examination (PE), including body weight and height, will be performed at Screening. A symptom directed physical examination will be performed at all other designated visits as clinically indicated. Weight will be collected at all visits and a PE will be performed as clinically indicated as outlined in [Table 1](#). Clinically significant changes from baseline will be documented in the source documentation and electronic case report forms (eCRFs) as adverse events.

ABT-414-Targeted Ophthalmologic Examinations (ABT-414-TOE)

The ABT-414 Targeted Ophthalmologic Examination (ABT-414 TOE) was designed for this study to systematically identify and grade objective findings of ABT-414-related eye toxicity and to assess for adverse effects potentially related to ocular steroid use. The ABT-414 TOE will be provided as study specific start up materials. Changes in the steroid potency of prophylactic eye drops to be used with ABT-414/placebo dosing will be based on corneal findings from the ABT-414-TOE assessments performed throughout the study, as described below in [Table 4](#).

Subjects will undergo ophthalmologic examinations as follows:

Screening: prior to starting chemoradiation

- Any clinically significant abnormal findings at Screening ophthalmologic examination are to be documented as part of the subject's medical history.

Chemoradiation Phase: within 7 days to 14 days after the 2nd and 3rd infusions of ABT-414/placebo

Adjuvant Phase: within 7 days prior to ABT-414/placebo dosing on Day 1 of Cycle 1, Cycle 2, and all odd-numbered cycles thereafter (Cycles 3, 5, 7, etc.) and at the 35-Day Follow-Up Visit.

Additional eye exams may be performed as needed throughout the study, including additional exams if evidence of microcystic keratopathy persists after the 35-Day Follow-Up Visit to monitor reversibility. A subset of sites will be asked to provide ophthalmic photography (e.g., slit lamp, confocal microscopy, Heidelberg Retina Tomographer [HRT3], etc.) of corneal abnormalities.

Ophthalmologic exams may be discontinued for subjects who have no evidence of eye toxicity on 2 consecutive examinations after being decreased to Level 1 eye drops.

Qualified medical personnel will perform the ophthalmologic examination, which will include assessments of visual acuity, intra-ocular pressure, funduscopy examination (at Screening, 35 Day Follow-Up Visit only), and slit lamp examination according to standard procedures of the ophthalmologist. The corneas will be evaluated via slit lamp at every exam to identify potential pathological changes. Grading on the ABT-414-TOE findings for "microcysts/edema" and "superficial punctate keratopathy" will be used to inform potential changes in the level of prophylactic steroid eye drops to be used with ABT-414/placebo dosing, as described in Section 5.5. Grading for these two items is as follows:

Microcysts/Edema

0	=	None
+0.5 (Trace)	=	Trace, localized epithelial haze
+1 (Mild)	=	Dull glass appearance that may include fine individual microcystic changes
+2 (Moderate)	=	Dull glass appearance of epithelium with large number of vacuoles with or without stromal edema
+3 (Severe)	=	Epithelial bullae and/or whorl keratopathy, localized or diffuse, with or without stromal striae

Superficial Punctate Keratopathy

0	=	None
+0.5 (Trace)	=	Trace (1 – 5 puncta)
+1 (Mild)	=	Mild (6 – 20 puncta)
+2 (Moderate)	=	Moderate (> 20 puncta, but countable)
+3 (Severe)	=	Severe (too many puncta to count)

Table 4: Ophthalmology Examination Schedule

STUDY VISIT/PERIOD*	EXAM REQUIRED?	COMMENTS
Screening	Yes	Establishes baseline assessment for corneal exam and visual acuity
Chemoradiation Phase		
Day 1, Week 5 (≤ 7 days before Week 5 ABT-414/placebo dose)	Yes	Do not decrease Level of eye drops until after the subject has received at least 2 eye exams
Day 1, Week 7 (7 – 14 days after Week 5 ABT-414/placebo dose)	Yes	--
Recovery Period		
No ophthalmology exam required	No	As-needed basis only
Adjuvant Phase		
Day 1, Cycle 1**	No	Exam not required if the subject had no corneal microcysts or ocular adverse events during or after the Chemoradiation Phase
Day 1, Cycle 2*	Yes	--
Day 1 of Cycles 3, 5, 7, etc.*	Yes***	Continue while subject is taking study drug (ABT-414/placebo)
35-Day Follow-Up Visit	Yes	
Ophthalmology exams required as scheduled for subjects on Level 2 – 4 eye drops.		

* Additional eye exams may be performed as needed. For eye toxicity considered by the investigator to be related to ABT-414, ophthalmology exams will be repeated until symptoms related to eye toxicity have resolved.

** Scheduled ophthalmology exams may be done at any time, up to 7 days before the scheduled date, prior to the scheduled infusion of ABT-414/placebo.

*** Eye exams may be discontinued for subjects who have no findings of ocular toxicity on 2 consecutive scheduled exams while on Level 1 (non-steroid) drops.

Adverse Event Reporting of ABT-414-TOE Findings

ABT-414-TOE reports will be reviewed by the Investigator (or medically qualified delegate). Examination records should be retained in the subject's source file. With the exception of the corneal findings described below, decisions on which findings, if any, from the ophthalmologic

examination or ABT-414-TOE report to be reported as adverse events will be made according to the Investigator's judgment. *Adverse events will be graded according to National Cancer Institute Common Terminology Criteria for Adverse Events (NCI CTCAE) v.4.0 criteria, as discussed in Section 7.2 and not according to the ABT-TOE grading system.*

To ensure consistent reporting of microcystic keratopathy, which is characteristic of ABT-414 but for which there is no Medical Dictionary for Regulatory Activities (MedDRA) preferred term or CTCAE adverse event term, any abnormal finding on the "corneal epithelium" and/or "superficial punctate keratopathy" fields of the ABT-414-TOE will be recorded as an adverse event, using the term "microcystic keratopathy." These events will be graded as shown in [Table 5](#), which is based on CTCAE criteria for "keratitis."

Table 5. Adverse Event Reporting in eCRF for Corneal Findings from the ABT-414-TOE

Corneal finding from ABT-414-TOE	Adverse Event Report for eCRF	
	Adverse Event Verbatim Term	CTCAE Grade
Microcysts/Edema OR Superficial punctate keratopathy	Microcystic keratopathy	1 – Asymptomatic or mild symptoms; clinical or diagnostic observations only; intervention not indicated
		2 – Symptomatic; medical intervention indicated (e.g., topical agents); limiting instrumental ADL
		3 – Decline in vision (worse than 20/40 but better than 20/200); limiting self care ADL
		4 – Perforation or blindness (20/200 or worse) in the affected eye

Vital Signs

Vital sign determinations of sitting blood pressure, heart rate and body temperature will be measured at all visits, as outlined in [Table 1](#). If possible, blood pressure and heart rate measurements should not immediately follow scheduled blood collections.

Blood pressure and pulse rate should be measured after the subject has been sitting for at least 3 minutes.

12-Lead Electrocardiogram (ECG)

A resting 12-lead ECG will be performed for all subjects as outlined in [Table 1](#) and [Table 2](#).

Each ECG will be printed and evaluated by an appropriately qualified physician (in consultation with a cardiologist if necessary) at the study site. A qualified physician will determine if any findings outside normal physiological variation are clinically significant, document the presence

or lack of findings and the clinical significance (if any) on the ECG report and then sign and date the ECG report.

The ECG tracings will be retained as source documentation in the subject's records at the study site. The baseline (Screening) ECG will be used to document baseline status of the subject so that safety comparisons can be made if necessary. Repeat ECGs will be performed whenever clinically necessary.

Karnofsky Performance Status

Karnofsky Performance Status (KPS)⁵ will be evaluated at the same time as the physical examinations. The status will be determined as:

- 100 – normal, no complaints, no signs of disease
- 90 – capable of normal activity, few symptoms or signs of disease
- 80 – normal activity with some difficulty, some symptoms or signs
- 70 – caring for self, not capable of normal activity or work
- 60 – requiring some help, can take care of most personal requirements
- 50 – requires help often, requires frequent medical care
- 40 – disabled, requires special care and help
- 30 – severely disabled, hospital admission indicated but no risk of death
- 20 – very ill, urgently requiring admission, requires supportive measures or treatment
- 10 – moribund, rapidly progressive fatal disease processes
- 0 – death

Pregnancy Test

For female subjects of childbearing potential, a serum pregnancy test will be performed ≤ 21 days before Day 1 of chemoradiation. A urine or serum pregnancy test will be done on Day 1 Week 1 if a serum pregnancy test was performed most recently more than 7 days before Day 1.

The test may be repeated at the discretion of the investigator at any time during the study. A lactating or pregnant female will not be eligible for participation in this study.

Clinical Laboratory Tests

All subjects will have the laboratory analyses performed as outlined in [Table 6](#). Laboratory samples will be assessed using a certified central laboratory, and these data will be used for all

data analysis. The central laboratory for this study will provide instructions regarding the collection, processing, and shipping of samples.

Clinical chemistry, hematology, and urinalysis labs will be collected according to the schedule shown in [Table 1](#) and [Table 2](#) (± 3 days). Screening labs will be performed within 21 days prior to Day 1 of the Chemoradiation Phase, and results must be reviewed by the Investigator or designee prior to dosing on Day 1. Screening labs may be repeated if clinically indicated to confirm eligibility.

The Principal Investigator or designee as noted on the delegation of authority log will review, initial and date all laboratory results. Any laboratory value outside the reference range that is considered clinically significant by the Investigator will be followed as appropriate. Clinically significant laboratory values will be recorded as adverse events if they meet the criteria as specified in [Section 7](#).

A certified local reference laboratory may perform laboratory testing as needed for immediate subject management. For laboratory results that are required per protocol to make study treatment decisions (e.g., to determine eligibility to continue TMZ), results from a certified local lab may be used if central results may not be available prior to dosing. However, the sample for central laboratory analysis should be drawn and sent as per the protocol schedule to be used in the data analysis. In the case of contradictory results, in which the local lab result supports eligibility or treatment decision that would be prohibited based on the central lab result, the local laboratory result must be recorded in the eCRF to be included in the data analysis. Other local laboratory values should not be captured in the eCRF. The appropriate documents will be collected for both the central and local laboratories, as needed.

For Day 22 hematology assessments during the Adjuvant Phase (performed when adjuvant TMZ treatment is ongoing) a certified local laboratory may be used alone without central testing. If a central laboratory result is not available for the Day 22 lab, the local lab results for platelet count and absolute neutrophil count (ANC) will be recorded in the eCRF.

Table 6. Clinical Laboratory Tests

Hematology	Clinical Chemistry	Urinalysis
Hematocrit	Blood urea nitrogen (BUN)	Specific gravity
Hemoglobin	Creatinine	Ketones
Red blood cell (RBC) count	Total bilirubin	pH
White blood cell (WBC) count	Serum glutamic-pyruvic transaminase (SGPT/ALT)	Protein
Neutrophils	Serum glutamic-oxaloacetic transaminase (SGOT/AST)	Blood
Bands (if detected)	Alkaline phosphatase (ALP)	Glucose
Lymphocytes	Gamma-glutamyl transferase (GGT)	Microscopic examination if dipstick results are positive
Monocytes	Sodium	
Basophils (if detected)	Potassium	
Eosinophils (if detected)	Calcium	
Absolute platelet count	Inorganic phosphorus	
Mean corpuscular volume (MCV)	Glucose	
Coagulation (screening Only)	Cholesterol	
Prothrombin time (PT)	Triglycerides	
Activated PartialThromboplastin Time (aPTT)	Total protein	
International normalized ratio (INR)	Uric Acid	
	Albumin	
	Lactate dehydrogenase (LDH)	
	Magnesium	
	Chloride	
	Bicarbonate	

For any laboratory test value outside the reference range that the Investigator considers to be clinically significant:

- The Investigator will follow the out-of-range value to a satisfactory clinical resolution.
- A laboratory test value that requires a subject to be discontinued or interrupted from any study treatment agent (ABT-414, TMZ or RT) or from the study, or requires a subject to receive treatment (medical intervention) will be recorded as an adverse event.

MRI and Clinical Assessment for Disease Progression

A brain MRI scan with and without contrast, performed at any time after diagnostic surgery or biopsy but prior to randomization, is required to serve as a baseline scan for RANO tumor response assessments. The most recent scan done prior to randomization will be used as the baseline scan. A baseline MRI must include the image sequences (T1 with and without contrast and T2 FLAIR) required for making RANO assessments. If a subject starts chemoradiation ≤ 28 days after surgery, the post-operative MRI scan (including an intraoperative or post-operative MRI scan) performed as part of standard care prior to Screening may be used as

the baseline scan for RANO assessments; if so, this scan must be included with the submission of scans for central imaging reviews. If the subject starts chemoradiation more than 28 days after surgery, then the baseline MRI must be performed within 21 (preferably fewer) days prior to Day 1 Week 1 of Chemoradiation and must allow sufficient time to revise the radiation therapy plan if needed due to a significant change in tumor since surgery.

Post-baseline MRIs with contrast will be obtained ≤ 14 days before Day 1 of each odd-numbered cycle (Cycles 1, 3, 5, etc.) of the Adjuvant Therapy Phase; approximately every 8 weeks of the Follow-Up Phase (≤ 14 days before each Follow-Up Visit), and at the Final Study Drug Visit (if the subject withdraws from the study prior to disease progression and has not had an MRI with contrast within the previous 3 weeks). At the discretion of the Investigator, MRI with contrast may be performed at additional times as clinically indicated or as needed to assess whether there has been progression of disease. If the subject discontinues study drug prior to disease progression, every effort should be made to acquire MRIs according to the same schedule while the subject is willing.

